9.3.2 SAFETY ENDPOINTS**Safety Endpoint 1:**

Occurrence of device-related Serious Adverse Events (SAEs) as reported on the case report forms.

Analysis cohort: Safety cohort.

Analysis methods:

The number of events, number of participants and proportion of participants experiencing any device-related SAE will be summarized by treatment arm. There are no hypothesis tests, but 95% CI for the proportion of participants with an event may be calculated.

Safety Endpoint 2:

Rate of device-related Adverse Events (AEs) as reported on the case report forms.

Analysis cohort: Safety cohort.

Analysis methods:

The number of events, number of participants and proportion of participants experiencing any device-related AE (including serious) will be summarized by treatment arm. There are no hypothesis tests, but 95% CI for the proportion of participants with an event may be calculated.

9.3.3 SECONDARY EFFECTIVENESS ENDPOINTS**Secondary Effectiveness Endpoint 1:**

The level of systolic unloading will be recorded for the Wave PRO based on the systolic peaks during compressions compared to baseline of the PPG data (before compressions and captured using the independent data acquisition system). Systolic unloading is the ratio of the systolic peak during compressions divided by baseline systolic peak. Previous studies that measured systolic pressure using coronary catheterization found that “peak aortic systolic pressure decreased 11% during ECP”⁴. Based on these findings, systolic unloading is expected to be similar when measured via PPG. Systolic unloading will be calculated as the ratio of the average systolic amplitude of the last 10 waveforms of baseline PPG before compressions divided by the average amplitude of the systolic amplitude of the first 10 waveforms during compressions.

Analysis cohort: mITT participants with paired data.

Analysis methods:

Descriptive statistics will be used to summarize systolic unloading including mean, standard deviation, median, and minimum and maximum. Additionally, the count and percentage of participants who have systolic unloading values $\geq 11\%$.

Secondary Effectiveness Endpoint 2:

Number of participants that complete 10 mins of each of the ECP devices (Wave PRO and predicate ECP device).

Analysis cohort: mITT participants with an attempt to receive Wave PRO ECP.

Analysis methods:

The count and proportion of participants that successfully completed the planned 10 min of Wave PRO ECP and the predicate ECP device will be summarized.

Secondary Effectiveness Endpoint 3:

Participant comfort level with the Wave PRO and predicate ECP device, assessed at the conclusion of each ECP session (i.e., using a Likert scale).

Analysis cohort: mITT participants

Analysis methods:

Descriptive statistics will be used to summarize the participant's comfort by ECP device.

Secondary Effectiveness Endpoint 4:

Time to set up a participant (i.e., sleeved up and sensors attached) and ready to start treatment.

Analysis cohort: mITT participants

Analysis methods:

Descriptive statistics will be used to summarize the setup time by ECP device.

Secondary Effectiveness Endpoint 5:

Participant preference for one of the two ECP systems (assuming 35 hours for a full course of ECP).

Analysis cohort: mITT participants

Analysis methods:

The count and proportion of participants that selected their preference as the Wave PRO vs all mITT participants.

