	
Performance/Effectiveness:
 
 ○ The level of systolic unloading for the Wave PRO based on the systolic peaks during compressions compared to baseline of the PPG data, captured using the independent data acquisition system. ○ Number of participants that complete 10 mins of each of the ECP devices (Wave PRO and predicate ECP device) ○ Participant comfort level with the Wave PRO and predicate ECP device, assessed at the conclusion of each ECP session ○ Time to set up a participant (i.e., sleeved up and sensors attached) and ready to start treatment ○ Participant preference for one of the two ECP systems (assuming 35 hours for a full course of ECP) 	
 ○ Systolic unloading is a corollary to DA ratio discussed above and is a suitable secondary endpoint for the same reasons – it is a direct and objective measure of the hemodynamic effect of ECP. ○ Proportion of participants that completed the 10-minute treatment sessions is an appropriate endpoint because it is a surrogate measure of the tolerability of the Wave PRO device compared to the predicate ECP device. ○ Participant comfort levels is an appropriate endpoint because it is measured on a standard scale and reflects direct patient response to the two devices. ○ Tracking participant setup time enables Pression to quantify ease of use compared to the predicate ECP technology. It is appropriate as it quantifies the amount of time that can be reduced from patient visits and can help maximize treatments that clinical entities can provide in a day. ○ Participant preference for either one of the ECP systems helps validate the Wave PRO as a viable product with the potential of being more accessible for a population that may have limited mobility due to chest pain.

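### Systolic unloading is defined by two reciprocal ratios, and the 11% responder cut-off is applied to them with no stated conversion to a percentage reduction

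*Combined protocol and SAP*

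**What the plan says.** All the relevant text is in section 9.3.3, Secondary Effectiveness Endpoint 1.

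- **Definition.** "Systolic unloading is the ratio of the systolic peak during compressions divided by baseline systolic peak".
- **Calculation.** A few sentences later, the computing rule is given in these terms: "ratio of the average systolic amplitude of the last 10 waveforms of baseline PPG before compressions divided by the average amplitude". The denominator is taken over the 10 earliest waveforms under compression.
- **Benchmark.** A cited catheterization study found that "peak aortic systolic pressure decreased 11% during ECP", and on that basis "systolic unloading is expected to be similar when measured via PPG".
- **Analysis.** Besides the mean, SD, median and range, the plan reports the "count and percentage of participants who have systolic unloading values" of at least 11%. The cohort is mITT participants with paired data.

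No other section settles the direction. Section 3 has only "The level of systolic unloading for the Wave PRO based on the systolic peaks during compressions compared to baseline of the PPG data", and the synopsis (1.1) uses the same wording. Section 4.1 names the two amplitudes to be recorded but gives no formula. Sections 6.3.3 and 10.1.7.3 describe output of the amplitudes, not of an unloading value.

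**The concern.** The definition and the calculation rule are reciprocals, so a value of 1.10 means a rise in systolic peak under one and a fall under the other. The reported mean, median and range cannot be interpreted without knowing which was used. The responder rule adds a second problem: its 11% is a percentage decrease, while the quantity it is applied to is defined as a ratio.

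This is the only systolic-unloading result planned, because section 4.1 excludes the calculation for the predicate. The study objective in the synopsis names systolic unloading beside the DA ratio, and section 3 presents it as direct evidence of hemodynamic effect. If the formula is left to the analyst, it may be chosen after the amplitudes have been seen.

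**Working it through.** **Inputs, all from section 9.3.3.** Let A = compression / baseline (the definition) and B = baseline / compression (the calculation rule), so B = 1/A. The cut-off is 11%, or 0.11.

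**Step 1: the benchmark on each scale.** An 11% decrease gives A = 1 − 0.11 = 0.89 and B = 1/0.89 = 1.124. Neither number is 11%; the cited figure corresponds to 1 − A.

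**Step 2: the rule read literally on the ratio.**

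| Change in systolic peak | A | B | A ≥ 0.11 | B ≥ 0.11 |
|---|---|---|---|---|
| 50% fall | 0.50 | 2.00 | yes | yes |
| 11% fall | 0.89 | 1.124 | yes | yes |
| No change | 1.00 | 1.00 | yes | yes |
| 11% rise | 1.11 | 0.90 | yes | yes |
| 20% rise | 1.20 | 0.83 | yes | yes |

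A misses the cut-off only if the amplitude falls by more than 1 − 0.11 = 89%. B misses it only if the amplitude rises more than 1/0.11 = 9.09-fold. Within any plausible range, the literal count does not distinguish unloading from no unloading.

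**Step 3: the rule read as a percentage reduction.** Each ratio suggests its own conversion.

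- From A: 1 − A ≥ 0.11 requires A ≤ 0.89, a fall of at least 11.0%.
- From B: B − 1 ≥ 0.11 requires B ≥ 1.11, so A ≤ 1/1.11 = 0.901, a fall of at least 1 − 0.901 = 9.9%.

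A participant with a 10% fall has 1 − A = 0.10 and is not a responder on the first conversion, but has B − 1 = 1/0.90 − 1 = 0.111 and is a responder on the second.

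**Step 4: size of the difference, under an assumption.** The documents give no SD for unloading. Suppose the percentage decrease is normally distributed with mean 11% and an SD between 5 and 20 percentage points. The responder proportion is then 50% with 1 − A and 52% to 59% with B − 1. The literal rule on A gives at least 99.995%. With a mean decrease of zero, the literal rule on A still gives at least 99.999%, against 1% to 29% with 1 − A.

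**Step 5: the summary statistics.** Take two illustrative participants with A = 0.80 and A = 1.20. The mean of A is (0.80 + 1.20)/2 = 1.00, which suggests no change. The mean of B is (1.25 + 0.833)/2 = 1.04, which suggests slight unloading. The choice of ratio therefore affects the reported mean as well as the responder count.

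**Step 6: the cohort.** Section 9.3.1 uses paired data to mean an average DA ratio from each system. Carried into Endpoint 1, that meaning would drop a participant with a complete Wave PRO recording who lacks a predicate value. If the term instead means a baseline and compression pair on Wave PRO, no one is lost for that reason. The text does not say which applies.

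**The case against.** The strongest reply is that the intent is clear. The 11% is introduced as a decrease, and PPG unloading is expected to be similar, so a competent analyst would work with a percentage reduction and obtain an informative count. That largely stands. A reader might infer from the literal arithmetic that the trial is bound to report 100% responders and that the endpoint is worthless. The documents do not support this: the result follows only if 11% is applied to a raw ratio, and even then extreme values are exceptions. What remains is that the conversion is unstated, the two natural conversions give different cut-offs, and the direction of the summary statistics is undefined.

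A reader might also infer that the first 10 compressed waveforms fall while Wave PRO is still tuning, and that the endpoint should use the 8th minute like the primary. Section 4.1 says tuning is automated but gives no duration. Section 4.2 says augmentation can appear almost at once, although it also refers to assessing initial response after five minutes. The first-10-waveform window is stated consistently in section 4.1, the Figure 1 notes and section 9.3.3. Nothing obliges a secondary endpoint to share the primary's window, and section 9.3.1 justifies minute 8 by movement late in the session, which is no argument against early beats.

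Finally, the endpoint is secondary, applies to Wave PRO only and has no hypothesis test. That is correct and limits the consequence.

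**Conclusion.** The concern holds as an inconsistency in the specification. Section 9.3.3 gives two reciprocal formulas for one endpoint and a cut-off that matches neither. Read literally, the responder count carries no information for any plausible amplitude change. Read as a percentage reduction, the cut-off is either an 11.0% or a 9.9% fall. The contradiction and these cut-offs follow from the text and exact arithmetic; only the responder proportions in Step 4 depend on an assumed distribution. The cohort point is conditional on how paired data is read.

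The primary non-inferiority test and the sample size are unaffected, and nothing is irrecoverable because both amplitudes are kept. This should be corrected, and before any amplitudes are analysed, because the study objective names systolic unloading.

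**What to change.** In section 9.3.3 and the Analysis Charter, replace both ratio definitions with one formula:

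unloading (%) = 100 × (mean baseline systolic amplitude − mean compression systolic amplitude) / mean baseline systolic amplitude.

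State that positive values mean unloading. Keep the planned windows (last 10 baseline waveforms, first 10 compression waveforms), apply the cut-off of at least 11% to this value, and report the summary statistics on the same scale.

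State that, for this endpoint, paired data means a baseline and a compression recording on Wave PRO, whether or not a predicate DA ratio is available.

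The cost is wording in the protocol/SAP and the Analysis Charter. Both amplitudes are already output and recorded (sections 4.1, 6.3.3 and 10.1.7.3), so no new data are needed.

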6.3 DATA ACQUISITION WAVE PRO

6.3.1 BIOPAC MP35 DATA ACQUISITION SYSTEM DESCRIPTION

The BIOPAC MP35 Data Acquisition system paired with the BSL 4.1 software will serve as the dedicated PPG waveform and data extraction system to acquire waveforms that will subsequently be used to calculate DA ratio and select secondary endpoints as a result of Wave PRO compressions. The MP35 is a four channel system with a 24-bit A/D sampling resolution. The MP35 is capable of recording 100,000 samples per second.

The BIOPAC SS4LA PPG Transducer, which connects to the 9-pin female DSUB connector on the MP35, will be attached to the participant’s finger using the built-in hook-and-loop strap to capture PPG signals. The SS4LA is a reflectance type PPG sensor that utilizes a matched infrared emitter and photo diode to detect changes in blood density due to blood pressure fluctuations. The emitter/detector wavelength is 860nm \pm 60nm, with a built-in low pass filter cutoff wavelength of 800nm.

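### The ≥11% systolic-unloading count applies a catheter-measured pressure fall to finger-PPG amplitude, a different quantity, so it cannot show unloading of the cited size

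*Combined protocol and SAP*

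**What the plan says.** Section 9.3.3, Secondary Effectiveness Endpoint 1, introduces its benchmark with "Previous studies that measured systolic pressure using coronary catheterization found that" and then cites the result: "peak aortic systolic pressure decreased 11% during ECP". The next sentence carries that figure over to the study's own measurement: "Based on these findings, systolic unloading is expected to be similar when measured via PPG". The planned analysis is a set of summary statistics plus "the count and percentage of participants who have systolic unloading values" of at least 11%.

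The study's measurement is a ratio of average systolic amplitudes from the BIOPAC finger sensor, taken over ten beats just before compressions and the first ten beats during them. Section 6.3.1 describes the sensor: "The SS4LA is a reflectance type PPG sensor that utilizes a matched infrared emitter and photo diode to detect changes in blood density".

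Three other places bear on the point:

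- The synopsis objective (Section 1.1) names systolic unloading beside the DA ratio as a measure of hemodynamic effect.
- Section 4.1 states that unloading is not calculated for the predicate device.
- Section 6.1.2 has blood pressure recorded in the rest period before Wave PRO compressions and again at the end of the session. It lists no reading while compressions run.

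**The concern.** The benchmark and the measurement are different quantities. One is the peak value of a pressure in the aorta. The other is the size of an optical pulse at the finger. A percentage change in one equals the same percentage change in the other only under particular conditions, and the plan neither states nor supports any.

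This matters for interpretation. Because the predicate has no unloading value, the 11% figure is the only yardstick in the plan for a quantity named in the objective. If the report says that a given percentage of participants reached at least 11% unloading, directly after citing the catheter result, a reader will take it as evidence that Wave PRO produces a pressure reduction of that size. A participant could meet the cut-off with a much smaller pressure fall, or miss it despite an 11% fall.

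**Working it through.** **What the documents supply.** The 11% comes from an outside study and cannot be re-derived here. The documents contain no conversion from PPG amplitude to pressure, no validation of one against the other, and no PPG-based source for 11%. The trial cannot supply the link itself, since pressure is recorded only before and after compressions. How amplitude is extracted from the waveform is left to an Analysis Charter that is not part of these documents.

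**Illustration of the scale problem.** The following are assumptions, not document figures: amplitude is proportional to pulse pressure, A = k(S − D), with k constant, and the resting pressures S/D are those in the table. If systolic pressure falls by 11% and diastolic pressure falls by d mmHg, then

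fractional amplitude fall = (0.11·S − d) / (S − D).

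With diastolic pressure unchanged (d = 0) this is 0.11·S/(S − D). In reverse, an 11% amplitude fall with diastolic pressure unchanged is a systolic pressure fall of 0.11·(S − D)/S.

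| Resting S/D (mmHg) | Amplitude fall for an 11% systolic pressure fall | Systolic pressure fall for an 11% amplitude fall |
|---|---|---|
| 110/70 | 12.1/40 = 30.2% | 4.4/110 = 4.0% |
| 120/80 | 13.2/40 = 33.0% | 4.4/120 = 3.7% |
| 130/70 | 14.3/60 = 23.8% | 6.6/130 = 5.1% |
| 140/80 | 15.4/60 = 25.7% | 6.6/140 = 4.7% |
| 150/90 | 16.5/60 = 27.5% | 6.6/150 = 4.4% |
| 150/70 | 16.5/80 = 20.6% | 8.8/150 = 5.9% |

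These six pairs give 21–33% and 3.7–5.9%. They are examples, not limits: a narrow pulse pressure such as 110/90 would give 12.1/20 = 60.5%, and in reverse 2.2/110 = 2.0%.

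**If diastolic pressure also changes.** Take 120/80, where an 11% systolic fall is 13.2 mmHg.

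- Diastolic also falls 11% (8.8 mmHg): (13.2 − 8.8)/40 = 11% amplitude fall.
- Diastolic falls by the same 13.2 mmHg: (13.2 − 13.2)/40 = 0% amplitude fall.

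Under this model, the same 11% systolic pressure fall can therefore appear as a 0%, 11% or 33% amplitude fall. The two scales agree when systolic and diastolic pressure fall by the same percentage, and nothing in the plan establishes that they do.

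**A neighbouring defect, kept separate.** The same section first says "Systolic unloading is the ratio of the systolic peak during compressions divided by baseline systolic peak", then sets out the calculation the other way up, with baseline in the numerator. An 11% amplitude fall is 0.89 on the first definition and 1/0.89 = 1.124 on the second, and no rule turns either into a percentage. Correcting this is necessary before any cut-off can be applied, but the benchmark would still belong to another quantity.

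**The case against.** **No decision rests on the count.** This stands. The only hypothesis test is on the DA ratio, and Endpoint 1 has no success criterion. A reader might infer that the trial's main conclusion is at risk, but the documents do not support that.

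**The plan never says that Wave PRO reproduces the catheter result.** Also true: it states an expectation and openly defines the endpoint from PPG data. The problem is that the cut-off invites the comparison. Section 3 says of unloading that "it is a direct and objective measure of the hemodynamic effect of ECP". One might read this as a claim to measure pressure directly, but it refers to hemodynamic effect, and it need not change for this point.

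**A within-person ratio cancels sensor gain.** It does, for a fixed gain. It would therefore go too far to dismiss the ratio as uncalibrated; the absence of calibration is in any case only inferred from silence. Cancelling gain does not turn amplitude into pressure, however. Nor does it remove a change in optical coupling or vascular tone when compressions start. If such a change scaled amplitude by 0.8 (an assumption), a participant with no pressure change would show a 20% apparent fall.

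**The sensor responds to pressure.** Section 6.3.1 does say the sensor works "to detect changes in blood density due to blood pressure fluctuations". That supports some association. It does not support equal percentage changes.

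**The arithmetic rests on outside assumptions.** It does, and a reader might infer from the 21–33% figures that the count understates unloading. The other scenarios show that no direction can be claimed.

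**Conclusion.** The concern holds as a matter of interpretation. An 11% fall in catheter-measured aortic pressure is used as a cut-off for a finger-PPG amplitude ratio on the strength of one unsupported sentence, and the trial collects nothing that could support it. The ≥11% count therefore cannot show systolic unloading of the cited size.

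The possible discrepancy is large: 21–33% against 11% for the six example pressures, and 3.7–5.9% against 11% in reverse. Those sizes depend on proportionality to pulse pressure, unchanged diastolic pressure and the chosen resting pressures. Without those assumptions, the size and direction of the error are unknown, and no corrected threshold can be computed from the documents. The primary non-inferiority conclusion is not touched.

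**What to change.** In Section 9.3.3, Secondary Effectiveness Endpoint 1:

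- Delete the sentence that expects PPG-measured unloading to be similar to the catheter finding.
- Drop the ≥11% count, or keep it only as a PPG-amplitude cut-off with no reference to the catheter finding.
- Define one quantity, 100 × (1 − compression amplitude / baseline amplitude), within participant. This also removes the conflict between the two ratio definitions.
- Report it with the summary statistics already planned plus a 95% CI for the mean, and label it a relative PPG amplitude change. The interval is descriptive: it describes amplitude and is open to the same changes in tone or coupling.
- State that no conclusion will be drawn about the size of any systolic pressure reduction.

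The change is to wording and to one descriptive output. No new data are needed and the sample size is unaffected. The sponsor loses, or relabels, one responder percentage.

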Study Objectives:	The study objective is to demonstrate substantial equivalence (non-inferiority) of the hemodynamic effect between the Wave PRO System and the predicate ECP device (ACS NCP-2) as measured by the diastolic augmentation (DA) ratio and systolic unloading.
Study Design:	
Participants will receive compressions from both ECP systems, one system at a time, in random order. Diastolic augmentation ratio will be evaluated for each participant on each test ECP system.
 
Participants will be aged 35+, with a history of mild to moderate coronary artery disease, serve as their own control, and meet the Inclusion Criteria and none of the Exclusion Criteria.
 
Total participant time is approximately 2.5 – 3 hours.
 
Data to be collected includes pulse photoplethysmography (PPG) and vital sign information. Demographic data and a device-related questionnaire will be collected.
 
Data Analysis will include calculating the average DA ratio for each ECP system from the pulse waveforms collected, for each participant. Systolic unloading level will be recorded for Wave PRO.

Number of Participants:	The required sample size is 44 participants with paired DA ratio data. Allowing up to 12% attrition , approximately 50 participants will be randomized to the ECP device order.
Number and Location of Investigational Sites:	One study site in the United States.
Expected Study Duration:	
Recruitment: 6 Weeks
 
Participant Follow-up: Phone call 1 day after the ECP session
 
Total Study Duration: 10 Weeks

Randomization:	The order in which the participant will receive the two ECP sessions will be randomized.
Safety Endpoint 1:	Occurrence of device-related Serious Adverse Events (SAEs).
Safety Endpoint 2:	
Rate of device-related Adverse Events (AEs).
 
Follow up questionnaire to address bruising, abrasion, soreness.

Primary Performance and/or Effectiveness Endpoint:	The average DA ratio for each ECP session, calculated from the eighth minute of compressions for each participant.

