9.2 POPULATIONS FOR ANALYSIS

The study has a single test population that will be enrolled according to the inclusion/exclusion criteria.

Intent-to-treat (ITT): All participants that are randomized.

Modified intent-to-treat (mITT): All participants that are randomized and receive any ECP compressions from either device. Group assignment will be the randomized treatment order even if therapy was delivered not according to randomization.

Safety Cohort: Same as the mITT. Only participants that receive any ECP compressions from either device will be included.

Per protocol (PP): Participants that are randomized and receive any ECP compressions from both devices, are treated as they are randomized, and have no major deviations (i.e., inclusion/exclusion criteria, randomization, affect participant safety or validity of primary endpoint).

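### Endpoint 2 compares 10-minute completion on two devices in a cohort that requires an attempt on Wave PRO only, so some first-session failures can be lost or misassigned

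*Combined protocol and SAP*

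**What the plan says.** Section 9.3.3 defines Endpoint 2 as completion of 10 minutes on each of the two devices. The summary is "The count and proportion of participants that successfully completed the planned 10 min of Wave PRO ECP and the predicate ECP device". The only analysis cohort given is "mITT participants with an attempt to receive Wave PRO ECP". No denominator is stated separately for the predicate.

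Section 3 gives the purpose of the endpoint: "it is a surrogate measure of the tolerability of the Wave PRO device compared to the predicate ECP device". It is therefore meant to be read as a comparison of the two devices.

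Three other provisions bear on it:

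- Section 1.1 (Randomization): "The order in which the participant will receive the two ECP sessions will be randomized". Either device can come first.
- Section 9.2 defines mITT as "All participants that are randomized and receive any ECP compressions from either device". One session on one device is enough to enter mITT.
- Section 7.2 allows a participant to withdraw, or to be removed, at any time. That includes the interval between sessions.

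Endpoints 3 and 4 in the same section are also summarized by device, and they use all mITT participants. No reason is given for the Wave PRO condition in Endpoint 2.

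**The concern.** A cohort conditioned on attempting Wave PRO suits the Wave PRO completion rate. It does not suit the predicate rate, because whether a predicate-first participant reaches Wave PRO can depend on how the predicate session went.

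Two mechanisms follow:

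1. A predicate-first participant starts the predicate, cannot finish and leaves. This person is in mITT but never attempts Wave PRO, so the predicate failure does not enter Endpoint 2.
2. A Wave PRO-first participant cannot finish Wave PRO and leaves. This person stays in the cohort. If the predicate proportion is taken over the whole cohort, he or she counts as a predicate non-completer without having started that device.

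Participants who stop early for intolerance are the ones this endpoint exists to count. What is at stake is the reported predicate completion rate, and so the tolerability comparison built on it.

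**Working it through.** **Inputs.** The documents give no completion or failure rates and no planned figure for this endpoint, so there is nothing of the plan's own to reproduce here. From Section 9.3.1 I take about 50 participants randomized. The plan's arithmetic for that number holds: 44 / (1 − 0.12) = 50. The following are assumptions:

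- 25 participants per order (h = 25).
- Failure probabilities fW (Wave PRO) and fP (predicate), the same in either session. I use 12% as an illustrative value; it equals the plan's attrition allowance but is not a failure rate stated anywhere.
- A share q of first-session failures who leave before the second device, taken as 0, 0.5 and 1.

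**Formulas.**

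- Endpoint 2 cohort (Wave PRO attempted): C = h + h(1 − fP·q)
- Predicate starters: S = h(1 − fW·q) + h
- Predicate completers: K = h(1 − fW·q)(1 − fP) + h(1 − fP)
- Predicate completion as written, whole cohort as denominator: K / C
- Predicate completion among starters: K / S = 1 − fP

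The reported rate is thus the rate among starters multiplied by S / C = (2 − fW·q) / (2 − fP·q). This factor is 1 when q = 0 or when fW = fP.

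**Results.**

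| fW | fP | q | K | C | As written | Among starters |
|---|---|---|---|---|---|---|
| 0 | 12% | 0 | 44 | 50 | 88.0% | 88.0% |
| 0 | 12% | 0.5 | 44 | 48.5 | 90.7% | 88.0% |
| 0 | 12% | 1 | 44 | 47 | 93.6% | 88.0% |
| 12% | 0 | 0 | 50 | 50 | 100% | 100% |
| 12% | 0 | 0.5 | 48.5 | 50 | 97.0% | 100% |
| 12% | 0 | 1 | 47 | 50 | 94.0% | 100% |
| 4% | 12% | 1 | 43.12 | 47 | 91.7% | 88.0% |
| 12% | 4% | 1 | 45.12 | 49 | 92.1% | 96.0% |
| 12% | 12% | 1 | 41.36 | 47 | 88.0% | 88.0% |

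In the third row, 6 predicate failures are expected (50 × 0.12). The 3 in the predicate-first half (25 × 0.12) are lost and the 3 in the Wave PRO-first half are kept. In the sixth row, 3 Wave PRO-first leavers count as predicate non-completers.

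**Effect on the comparison.** The cohort contains everyone who attempts Wave PRO, so Wave PRO completion stays at 1 − fW. In the third row the reported gap is 100 − 93.6 = 6.4 points, when 100 − 88.0 = 12.0 points is correct. In the sixth row it is 94.0 − 88.0 = 6.0 points, when 100 − 88.0 = 12.0 is correct. In both cases the difference between the devices is understated.

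**A different denominator.** Suppose the predicate proportion uses cohort members who started the predicate. The second mechanism then disappears and the first stands alone. At 12% on both devices and q = 1, the rate is 41.36 / (22 + 22) = 94.0%, against 88.0% among starters.

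**The case against.** The strongest reply is that nothing may go wrong. Section 7.1 treats stopping a procedure separately from leaving the study in Section 7.2. The missing-data text in Section 9.3.1 foresees participants unable to tolerate both devices, which implies that failing the first does not end participation. If every first-session failure goes on to the second device, the cohort as written gives the right answer. This stands, and it is why the size is given as a range starting at zero.

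The second mechanism depends on a denominator that the plan does not state. The endpoint could also be read as counting participants who completed both devices, in which case a Wave PRO-first leaver is properly a non-completer. This stands too. The first mechanism survives either reading.

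Section 9.3.1 says that participants unable to tolerate either therapy will be summarized separately, Section 7.1 requires a documented reason for any procedure not completed, and the Safety Cohort keeps everyone who received compressions. These keep such participants visible in the trial. They do not change the Endpoint 2 proportion. The separate summary sits under the primary endpoint, and its wording leaves open whether one device or both is meant.

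A reader might infer that predicate failures in general are dropped and Wave PRO failures in general are charged to the predicate. The text does not support that. Wave PRO-first participants who fail the predicate stay in, as do predicate-first participants who fail it and still attempt Wave PRO.

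A reader might also extend the criticism to Endpoint 5, which counts "participants that selected their preference as the Wave PRO vs all mITT participants". That denominator is explicit. It treats anyone who expresses no preference as not choosing Wave PRO, which is conservative for the sponsor's device. It is not an error.

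**Conclusion.** The point holds in a limited form. A two-device comparison has a cohort tied to one device, by a stated rule rather than an omission. Under the assumptions of 25 per order and a 12% failure rate on one device only, predicate completion is overstated by 0 to 5.6 points (93.6 − 88.0) when the predicate is the less tolerable device. When Wave PRO is the less tolerable one, and the whole cohort is the denominator, it is understated by 0 to 6.0 points (100 − 94.0). The size depends on how many first-session failures leave, which the documents do not predict.

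The bias has no fixed direction for the predicate rate, and a reader should not infer that the rule favors Wave PRO. The two errors offset when failure rates are equal and the whole cohort is the denominator. That is little comfort, because the error appears as the devices' tolerability diverges, which is what the endpoint is meant to show.

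The consequence is confined to one descriptive secondary endpoint without a hypothesis test. The primary analysis, the sample size and the non-inferiority conclusion are untouched. The wording should be corrected, but it does not threaten the trial.

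**What to change.** In Section 9.3.3, Endpoint 2, replace the single cohort with a denominator for each device: mITT participants in whom compressions on that device were started. Then:

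- report the count and proportion completing 10 minutes for each device on its own denominator, overall and by sequence;
- for participants who started both devices, add the paired 2×2 table of completion on Wave PRO by completion on the predicate, which also answers the reading that both sessions must be completed.

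The cost is analysis-plan wording and one or two further descriptive tables. No change to sample size or primary analysis is needed. The change should be made before the completion data are reviewed, so that results cannot influence the choice of denominator.
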